1. EXECUTIVE SUMMARY

Antenatal care programmes as currently practised originate from models developed in Europe in the early decades of this century. The number of visits and the core activities remain practically unchanged and unevaluated, and new technologies which have been incorporated have seldom been scientifically assessed. Furthermore, the coverage of this traditional antenatal care in developing countries is very low and tends to be used by those women at lowest risk. It is unrealistic to expect that these countries will be able to expand this model of antenatal care to cover all women. A recent UNFPA report (Sakik, 1991) recognized that the required increase in the coverage and quality of MCH/FP services will have to be reached within the existing strategies and technologies and will likely have to be achieved with less than adequate resources. Hence, there is an urgent need, particularly in developing countries, for the evaluation of antenatal care effectiveness and for the study and identification of a scientifically proven package which can be offered to all pregnant women in these countries. This will complement efforts being made to evaluate specific perinatal activities.

The World Health Organization and collaborating institutions in developing countries have started conducting a randomized controlled trial to evaluate the impact of an improved and rational programme of antenatal care on the health of mothers and newborns. The duration of the entire study is 51 months.

The antenatal care programme presently in use in developing countries varies from one site to another, but is usually based on developed countries' practices. The recommended number of visits is typically eight to twelve, although the actual average number for those who attend at all will be closer to four.

The core of the new, improved programme of antenatal care consists of four visits which include only activities scientifically demonstrated to be effective in improving pregnancy and maternal and newborn outcomes. Specific interventions are included in each of these four visits. Health education and information for the mother are a part of each visit, stressing the

danger signs of complication during pregnancy and actions to be taken should they occur. The protocol specifies tests to be done at each visit and the specific actions for the different test results.

The proposed study enrolls approximately 5,000 women in each of four institutions over an average period of 18 months. There are a total of 56 antenatal care units, randomly allocated to provide either the new programme of antenatal care or the programme presently in use. Each group of antenatal care units is expected to be similar in terms of number of clients served, population characteristics (race, ethnicity, religion, socio-economic status, general health conditions), and levels of perinatal outcomes. Women are recruited as they present for antenatal care.

The two programmes of antenatal care will be evaluated in terms of severe maternal and perinatal morbidity. Since maternal mortality is a rare event, it is not feasible to conduct a study to demonstrate an impact of health care on it, and surrogate measures will therefore be used. The sample size calculation is based on the anticipated impact on selected maternal and newborn morbidity indicators. (Assuming that these indicators will have on average an incidence of 100 per 1,000 live births in participating centres, the study is designed to detect a 18% change).

The impact of the two programmes on maternal health will be compared in terms of specific morbidities, their severity, and general measures of morbidity, such as days in hospital and amount of resources consumed during hospital stay.

The impact on neonatal health will be assessed in terms of perinatal and neonatal morbidity, birth weight, gestational age and incidence of specific morbidities, as well as more general measures of neonatal status such as days in special care, including intensive care (where available), condition at discharge and hospital resources consumed. Where there is evidence that the resources required by the programmes differ, the cost effectiveness of programmes of care will be evaluated in different settings.

In addition, the two programmes of antenatal care will be compared in terms of process variables, such as average duration of contact between patient and care provider, average waiting time of patients, cost of antenatal care per pregnancy, patient and provider satisfaction with the services and perceived quality of care in a random sample of the population studied.

The study is coordinated by WHO in collaboration with the local institutions in Argentina, Cuba, Saudi Arabia and Thailand.

If the new programme of antenatal care is found to be more effective in preventing neonatal and maternal morbidity, and/or it is found to be less expensive than the traditional programme at the same level of pregnancy outcome, considering that users and providers are more satisfied with the new model, WHO will develop and circulate recommendations for antenatal care to governments and other agencies. It is expected that the new system will allow countries to maximize their resources and concentrate them in the most rational and effective way.

This report describes a descriptive result of a study conducted in Khon Kaen, Thailand.

This is a part of a large multiclinic, multisite, cluster randomized controlled trial. The other 3 sites include Rosario, Argentina, Havana, Cuba and Jeddha, Saudi Arabia. Twelve antenatal care clinics in 12 district hospitals were randomly assigned into 2 groups. Six clinics in the intervention group offered a new model of antenatal care while the other 6 clinics in the control group offered a traditional antenatal care. Recruitment of subjects was from May 1, 1996 to April 30, 1997. Follow up of the recruited subjects was done until October 31, 1997. All the data were entered and updated by the local coordination unit in Khon Kaen and transferred monthly to WHO in Geneva by e-mail. The expected number of subjects from Khon Kaen, Thailand was 6000. The total sample size from 4 sites was about 20000 subjects.

Six thousand seven hundred and sixty five subjects were recruited, 3449 and 3316 subjects in the intervention and control groups respectively. There were 182 missing subjects, a rate of 2.7%, leaving 6583 subjects for data analysis. Among 3379 subjects available for analysis in the intervention group, 3053 (90.3%) subjects were classified to be low risk and eligible for a new basic antenatal care model. The average age was 24.5 years with 18.7% teenage pregnancy. A majority of subjects attended primary school education. There were very few subjects who smoked or used known substance abuse. About 40% of subjects were primigravida. Rh isoimmunization was very rare. There were 182 (2.7%) abortions. More than 90% of the subjects received completed tetanus immunization. Most subjects (95.7%) received iron supplementation. During antenatal care, 144 (2.3%) subjects were referred to a higher level of care, while 180 (2.8%) subjects required antenatal hospital admission. The prevalence of severe anemia (Hb < 90 g/l) were 4.7% and 6.4% in the antenatal and postpartum period respectively. There were 113 (1.8%) subjects with severe urinary tract infection. There were 60 (0.9%) subjects with pregnancy induced hypertension (PIH) but only 26 (0.4%) required treatment. The incidence of maternal morbidity index indicator* was 8.3%. The low birth weight rate was 9.0%. Eight women died, giving a maternal mortality rate of 0.12%. There were 6400 births with 100 (14.5/1000) fetal deaths and 42 (6.7/1000) neonatal deaths. The perinatal mortality rate was 22.2 per 1000 births.

The result of the comparison between the new antenatal care model and the traditional model will be submitted to MotherCare when data from the other 3 sites are available and combined for statistical analysis which is expected to be available in late 1999.

* Maternal morbidity index indicator is defined as the presence of one of the following severe maternal conditions : proteinuric - preclampsia, eclampsia or severe hypertension (> 160/110 mm Hg) during pregnancy or within 24 hours of delivery; postpartum anemia < 90 g/l of hemoglobin and severe urinary tract infection/pyelonephritis, defined as requiring antibiotic treatment or hospitalization.

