3.2 Objectives

The objectives of the whole project are :

- To conduct a multicentre, multinational controlled trial comparing two models of antenatal care;
- To establish the relative merits of each model;
- To test whether the proposed new model is more effective than the traditional multivisit model with regard to maternal morbidity and perinatal morbidity and mortality, cost and satisfaction.

The objective of the study at Khon Kaen, Thailand is to participate in the high quality multicentre, multinational randomized controlled trial comparing two models of antenatal care. It was expected to contribute about 6,000 subjects for the whole project.

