4.2 Study Design

A randomized controlled trial is necessary for the evaluation of the effect of antenatal care on pregnancy outcome specifically to control for bias in patient selection, as has occurred in most of the observational studies. Women delivering preterm infants have less "gestational time" for more prenatal visits, thus making the association between prenatal care and prematurity stronger. Conversely, late initiators of prenatal care have fewer preterm newborns because they are still pregnant after 36 weeks, thereby weakening the effect. Women with known medical complications tend to attend early and have more visits but also have more preterm/IUGR infants, producing the U-shaped curve of the association (more care, more preterm/IUGR). Finally, healthy well-educated women who have very low risk for preterm-IUGR will also attend early, have many visits and make the association stronger. All these recognized selection biases, as well as those presently ignored, can only be controlled by a large randomized controlled study design.

The study is a large, multiclinic, multisite, randomized controlled trial of two different models of antenatal care; a new model of care will be compared with the traditional recommended model as it is presently implemented in the selected sites. Maternal, fetal, perinatal, cost and satisfaction end-points will be compared. The trial are conducted in four sites worldwide; each study site will include between ten and twelve antenatal care clinics

[figure not shown]
(clusters). All women attending each clinic will be included in the assessment of the clinic end-points and will be registered on their first antenatal visit and followed until discharge from the hospital post-partum. Deliveries from all ANC clinics (intervention and control) in a particular study site should occur at the selected medical facilities (Figure 1). Antenatal care clinics (cluster randomization), not individual women, will be randomized to the two arms of the study. Randomization will be stratified within each geographic study site by the size of the patient population enrolled in each clinic or cluster (large, medium and small clusters).

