ρ = intracluster correlation coefficient; shaded ρ was obtained using data from hospitals and clinics from one of the study sites (Villar et al, 1994).

O.R. - odds ratio

* O.R. = 1.16 corresponds to $P_c = 0.10$ and $P_t = 0.114$

** O.R. = 1.18 corresponds to $P_c = 0.10$ and $P_t = 0.116$

total 21,000 patients (Table 7c). Thus, the study will aim at recruiting at least four study sites which can provide twelve antenatal care clinics of 450 pregnancies during no more than 18 months of patient enrollment.

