4.10.1 Final analysis

All principal analyses will be based on the clusters as allocated in the randomization to the two programmes of antenatal care ("intention to treat"). Information will be presented for the following areas:

- sample description by intervention/control and site;

- characteristics of women at first antenatal visit in the intervention and control groups: overall and by stratum;
- analysis of the content of the intervention and the antenatal care received in the control group:
- evaluation of process variables;
- evaluation of primary outcomes;
- evaluation of secondary outcomes;
- stratified analysis of primary outcomes by the following a priori selected predicting variables:
 1. Size of the clinics: small, medium, large (following definitions of stratum);
 2. Low risk-high risk;
 3. Gestational age at first visit (early vs late attendance);
 4. Singleton-multiple pregnancies.

The study design will generate approximately 50 clinics with a number between 450 and 500 patients each. The primary question of the trial is whether or not patients seen in the experimental clinics differ from those in control clinics with respect to the primary outcomes of the study (see Section 4.7: Outcome Variables).

Since sample size calculation were conducted using the usual Mantel-Haenszel statistics modified to adjust for the cluster design, data analysis also can be performed using women as the analytical unit (individual rather than cluster analytical unit). The use of the mother as analytic unit allows for exploring secondary analysis such as the relationship between maternal baseline characteristics and other outcomes using a generalized equation approach (Liang and Zeger 1986). The main analytic technique will be an application of the Manatel-Haenszel test adapted to the cluster design (Donner 1992).

Appendix III presents a set of dummy tables to be completed during the analysis using cluster as the analytic unit. Accordingly, data will be collected primarily to complete these tables.

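### The protocol gives incompatible trial sizes, and its 90% power belongs to one of them, with no allowance for loss; for 20,000 recruits about 88-89% follows if all sites lose as Khon Kaen did

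*Protocol*

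**What the plan says.** The size of the trial is described in four places.

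- **Executive Summary:** "There are a total of 56 antenatal care units", randomly allocated to the two programmes. The study "enrolls approximately 5,000 women in each of four institutions", and later: "The total sample size from 4 sites was about 20000 subjects".
- **Sections 4.2 and 4.2.2:** "each study site will include between ten and twelve antenatal care clinics". The site criteria in 4.2.2 repeat the range of 10 to 12, and the clinic criteria accept 300 to 500 new patients per clinic.
- **Section 4.8.2:** for 90% power, twelve clinics of 450 pregnancies in each of four sites, summarised as "total 21,000 patients (Table 7c"). The matching entry of Table 7c is N = 20,780.
- **Section 4.10.1:** "approximately 50 clinics with a number between 450 and 500 patients each".

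Section 4.8.1 lists loss to follow-up among the factors that influence sample size. Section 4.8.2 sizes the trial on low birth weight. Section 4.2.5 enrols every woman at her first antenatal visit, whatever her history or condition. The third objective in section 3.2 is "To test whether the proposed new model is more effective than the traditional multivisit model".

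**The concern.** In a cluster trial the number of randomised units is a basic design figure. Section 4.2.2 itself says that the number of clusters matters more than their size. The power depends on the number of clinics, the women per clinic and the women with an outcome, and the document does not fix any of the three.

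The 90% target also has a stated purpose. Section 4.8.2 introduces it to limit the chance of calling the two models equivalent when they are not. Anyone reading a null result will rely on that figure, so it should belong to the trial actually described and count the women who can contribute the outcome. Low birth weight needs a birth, while enrolment takes place months earlier.

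**Working it through.** **1. Set the sizes side by side.**

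| Place | Clinics | Women |
|---|---|---|
| Executive Summary | 56 | 4 x 5,000 = 20,000 |
| 4.2, 4.2.2 | 4 x (10 to 12) = 40 to 48 | not totalled |
| 4.8.2 | 4 x 12 = 48 (implied) | 21,000 (Table 7c: 20,780) |
| 4.10.1 | about 50 | 50 x (450 to 500) = 22,500 to 25,000 |

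Khon Kaen has 12 clinics (Table 1). A total of 56 would need the other three sites to average (56 - 12)/3 = 14.7 clinics, above the stated maximum of 12.

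**2. Reproduce the protocol's figure.** Inputs from section 4.8.2: control rates .07, .09, .11 and .13 in four equal strata, odds ratio 1.18, two-sided alpha .05 (z = 1.96), intracluster correlation (rho) .00065 as the tables use it. For 90% power I take z = 1.282. With pc and pi the control and intervention rates in a stratum and p their mean:

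N0 = 8 x { [1.96 x sqrt(sum of 2p(1-p)) + z_beta x sqrt(sum of pc(1-pc) + pi(1-pi))] / sum of (pi - pc) }^2

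N = N0 x DE, where DE = 1 + (m - 1) x rho and m is women per clinic.

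- rho = 0: N0 = 12,016 at 80% power and 16,085 at 90%. Both are the printed values.
- m = 450, rho = .00065: DE = 1 + 449 x .00065 = 1.29185, and N = 16,085 x 1.29185 = 20,779 (printed 20,780).
- m = 300 gives 19,211 and m = 600 gives 22,348, both as printed.

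The formula is therefore the protocol's own, and no loss factor sits in it.

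**3. Loss seen in the document.** Khon Kaen (Table 17): 182 recruits without a summary form, 182 abortions, 23 not pregnant and 24 moved away. That is 411 of 6,765, or 6.1%. The remainder, 6,354, is the denominator of Tables 24 and 25. Applied to 20,000 recruits: 20,000 x 6,354/6,765 = about 18,785 deliveries.

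**4. Power at the stated layouts.** Power = Phi(3.242 x sqrt(N/(DE x N0)) - 1.96), with m = N/number of clinics. N0 at 90% is 16,085 for odds ratio 1.18. The same formula gives N0 = 18,335 for odds ratio 1/1.18.

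| Women with outcome | Clinics | m | DE | OR 1.18 | OR 1/1.18 |
|---|---|---|---|---|---|
| 20,000 (no loss) | 48 | 417 | 1.270 | 89.4% | 85.2% |
| 20,000 (no loss) | 56 | 357 | 1.231 | 90.3% | 86.2% |
| 18,785 (6.1% loss) | 48 | 391 | 1.254 | 87.9% | 83.4% |
| 18,785 (6.1% loss) | 56 | 335 | 1.217 | 88.8% | 84.5% |

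Worked line, 18,785 in 48 clinics: 18,785/(1.2537 x 16,085) = 0.9315, its square root is 0.9651, and 3.242 x 0.9651 - 1.96 = 1.169, so Phi = 87.9%.

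**5. Sensitivity.** With 10% loss, power for odds ratio 1.18 is 86.8% (48 clinics) to 87.7% (56 clinics). The intracluster correlation matters more: 20,000 women with outcomes give 86-87% at .001 and 76-79% at .002, both values that Table 7c also tabulates.

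**The case against.** **The power is nearly right.** The sizes are given as approximate and the 90% as something the investigators would like to have. Table 7c needs only 19,211 women at 300 per clinic, a size that section 4.2.2 accepts. This stands. A reader might infer that 90% power fits only N = 20,780, so that 20,000 women cannot reach it. The document does not support that: 20,780 is tied to 450 per clinic, and 20,000 women with outcomes in 56 clinics give 90.3%.

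**Losses shrink clinics; they do not remove them.** A reader who removes 6.1% of women but keeps 450 per clinic would get 86.9%, and about 82% for a reduction. Those figures are too low for any layout of 48 to 56 clinics.

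**21,000 is not an arithmetic slip.** It is tempting to correct it to 48 x 450 = 21,600. But 21,000 is Table 7c's 20,780 rounded, and the table notes say that clinics times size matches N only approximately because clinic numbers were rounded up.

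**Sizing for an increase was deliberate.** Section 4.8.1 says the programme must be shown not to increase either primary outcome, and the test is two-sided. That explains the choice of odds ratio. What remains is that section 3.2 states superiority, and no power is given in that direction.

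**Khon Kaen over-recruited.** It enrolled 6,765 against 6,000 expected, and its 6,354 deliveries exceed that plan. Likewise the size in section 4.10.1 would give 90.9-92.9% after 6.1% loss. Both are true. They show that the answer depends on which stated size is meant, which is the point at issue.

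**A fifth country could explain 56.** Section 4.8.2 mentions the possibility, and five sites of 10 to 12 clinics would cover 56. However, the Executive Summary pairs 56 with four institutions and names four countries.

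**Conclusion.** The contradiction in clinics and women is real and cannot be put down to rounding. The 90% power is correct for the cell it comes from, but that cell is neither the 56 clinics and 20,000 women of the Executive Summary nor the 50 clinics of section 4.10.1, and it counts only women with an outcome.

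The effect on power is modest. For odds ratio 1.18, 20,000 women with outcomes are within a point of 90% in 48 to 56 clinics. After 6.1% loss the figure is 87.9-88.8%, a shortfall of about 1 to 2 points. For a reduction of the same odds ratio it is 83.4-84.5%.

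This rests on three assumptions: that the other sites lose the same share as Khon Kaen, since the protocol gives no planning figure; that the intracluster correlation is .00065 as tabulated; and that clinics are of equal size, as in the protocol's formula. The result does not show that the trial is too small, and it does not call for more patients.

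**What to change.** State one design in the Executive Summary and sections 4.2, 4.2.2, 4.8.2 and 4.10.1: clinics per site and per arm, women per clinic, women recruited, and deliveries expected after a stated loss allowance.

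In section 4.8.2, restate the power for delivered women at that design. With 20,000 recruits in 48 to 56 clinics and 6.1% loss, this is about 88-89% for odds ratio 1.18. Say that the 90% in Table 7c refers to detecting an increase, and give the figure for odds ratio 1/1.18 beside it, about 83-85% under the same conditions, so that the objective in section 3.2 has its own power statement.

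The 21,000 may stay if it is labelled as the rounded Table 7c value. The cost is a text correction and a slightly less favourable stated power.

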2. INTRODUCTION

Antenatal care programmes, as currently practised, originate from models developed in the early decades of this century in Europe, notably the UK. The core of these early models remains practically unchanged in current programmes, although, as medical knowledge and technology have evolved, new technologies for screening for disease and primary and secondary prevention have been added to routine antenatal care in developed countries. Unfortunately, these new components and the timing of visits have most often been introduced without proper scientific evaluation (Rosen et al., 1991; Fink et al., 1992; Johnstone et al., 1993).

These models for antenatal care contain a substantial number of visits for the mothers – as many as 16 visits – with little or no distinction between high and low-risk mothers. Recently, cost-benefit aspects of antenatal care have been addressed in several countries, and attempts are being made to reduce costs for clients and the health care services (Anon, 1986; Rosen et al., 1991).

To a large extent, developing countries have in theory adopted the antenatal programmes of the developed countries with only minor adjustments pertaining to endemic diseases. In many of these countries where resources for reproductive health care are sparse or used less than efficiently (Sundari, 1992; Fathalla and Rosenfield, 1992) and fertility rates are still high, the cost benefit of antenatal care as practised must be questioned. The care often consists of irregularly spaced visits with long waiting time and poor feedback to mothers, and there is little communication between the antenatal care clinics and the obstetric departments and maternity units.

Because of time constraints, the visits tend to be of a ritualistic nature rather than rational health care, as is demonstrated by recent evaluation of the activities of prenatal care in three large maternities in Latin America (Kestler, 1992). Normal pregnant women spent an average of 62 to 228 minutes in the clinics, with only nine to twelve of those minutes with the doctor. The doctor's interview lasted a mean of five minutes. No time is routinely

devoted to activities of women's most important concerns, such as the explanation of procedures and involvement of mothers in these procedures (Drew et al., 1989). However, in most developing countries, women attending prenatal care do not receive all the benefits possible from these visits. For example, tetanus immunization is not provided to a large proportion of women attending prenatal care although this is recommended in all programmes (Buekens, 1990; Buekens, 1995).

For most developing countries, the validity of the content and the rationale for frequency and timing of visits have not been evaluated at all. The few observations made have questioned the impact of antenatal care on maternal and perinatal morbidity and mortality (Moller et al., 1991; Rooney and Graham, 1991). It is worth noting that the lack of evaluation of antenatal care is not exclusive to developing countries (Starfield, 1985). The recent US Public Health Service Expert Panel on the Content of Prenatal Care noted in their review "the literature on prenatal care activities was often limited, and many studies were conducted without maximal scientific rigor" (Rosen et al., 1991). Similar conclusions were made by the European panel (Lindmark and Crattingius, 1991).

The need for randomized controlled trials on procedures and examinations included in currently practised antenatal care, has been identified (Steer, 1993). A recent extensive review of the literature concluded that "carefully controlled evaluations of the content, number and timing of prenatal care visits for women with differing medical and social risk are essential" (Fink et al., 1992). Such trials can establish minimal levels of care for women at low risk through comparison with less frequent or less intense prenatal care to standard care (Fiscella, 1995).

The means whereby antenatal care prevents maternal and perinatal mortality and morbidity is logically complex. Few of the procedures commonly undertaken during antenatal care have a major impact on morbidity or mortality, and some may have no effect. For others, there can be no impact unless other elements are also in place and functional; for example, identifying preeclampsia has no impact unless affordable and effective treatment is instituted or available; identifying the risk of postpartum hemorrhage has no impact if

institutional delivery is not sought, unavailable or ineffective. To further complicate the evaluation of the effect of prenatal care on perinatal mortality, there is a different effect across populations. In Indonesia, among normal birth weight infants, prenatal care had more impact on perinatal mortality than maternal education, used as an a priori indicator for socioeconomic level (Bernard & Sastrawinata, 1985). Conversely, in New York City, prenatal care has less impact on perinatal mortality than maternal education (Paneth et al., 1982).

Epidemiological studies tend to show that women who receive antenatal care have lower maternal and perinatal mortality (U.S. Congress, 1988; Greenberg, 1983; Fiscella, 1995). Epidemiological studies have also shown that there is an association between the number of prenatal visits and gestational age at the initiation of care with pregnancy outcomes after controlling for confounding factors, such as length of gestation (Gortmaker, 1979; Ryan, 1980; Quick, 1981).

Because of this relationship in non-controlled studies, the importance of antenatal care in preventing mortality and morbidity is emphasized. Because of the suggested dose-response effect, many maternal health programmes seek to increase the quantity of antenatal care provided. Recently, however, attention has been given to the essential elements of the prenatal care package, in an effort of ensure that quality is not overlooked in favour of quantity. Consideration is also being given to whether more effective antenatal care could be provided with fewer visits, and when these fewer visits are focused on the elements most likely to have an impact on mortality and morbidity; in other words, to stress quality at the expense of quantity. In principle, this should be more effective as well as less expensive. Emphasis is made on the evaluation of a comprehensive package of antenatal care, rather than individual clinical interventions, because evidence demonstrates the disparities in pregnancy outcomes between social group are due to all major maternal conditions and not to single pathologies (Kempe, 1992). Furthermore, the interactive nature of antenatal interventions and the multicausal characteristics of the leading negative outcomes to be prevented point toward a multiplicative effect of the components of antenatal care.

The concept of antenatal care has been generally recognized as a very good model of preventive health care. In theory, a series of health examinations with predefined content should enable health personnel to uncover ailments and other conditions in the mother and her fetus(es) which may threaten the pregnancy and its outcome. The conditions may then be treated or monitored to secure a better outcome. Planning for a safe delivery is an integral part of antenatal care. In a wider context, antenatal care should embrace the social environment, as well as the medical aspects of pregnancy. It is also one of the few situations in which healthy women will have contact with the health care system, allowing for other preventive interventions (Rosen et al., 1991).

In currently applied antenatal care programmes, the basic philosophy is that, in normal cases, the visits should become gradually more frequent as pregnancy advances, starting with monthly check-ups to week 28, followed by visits at two-weekly intervals up to week 36, and weekly visits thereafter. The basic content of care at each visit has not changed substantially over the years, although modern technology has led to the introduction of several new elements in pregnancy surveillance, the typical examples being Doppler echocardiography, sonographic imaging of the uterus and its contents, and biochemical and cell culturing techniques for the identification of abnormal fetuses or threatened by malnourishment.

In countries where women traditionally or on advice attend the antenatal services early in pregnancy, the average actual number of visits is ten to twelve, and attendance rates are nearly 100% (WHO, 1989). In the European Economical Community countries, Luxemburg is an exception with an average of only five visits, while its neighbour, the Netherlands, has between 12 to 14 (Blondel, 1986). A recent survey in Scotland revealed that the average number of antenatal visits for women with low risk pregnancies was 14 (Howie et al., 1991). In Sweden, the recommended number is 16 (Kamper-Jorgensen et al., 1986) and in Finland even women make 15.2 antenatal visits of which 2.2 visits were to a hospital clinic (Gissler, 1994). For the USA, providers including midwives, tend to exceed the American College of Obstetricians and Gynecology's guideline for the recommended number of prenatal visits (Baldwin, 1994).

In spite of the similarity of antenatal care programmes, surveys reveal that both the quantity and the quality vary. Services are, in theory, available to all pregnant women, either through private health care or through public programmes. Social inequality has been demonstrated in England and Wales, and in France, for late attendance and number of antenatal care visits (Garcia et al., 1989). In the USA, there are several barriers to utilization of services by women with low socio-economic status (Buekens, 1990).

Considerable resources are spent on antenatal care in industrialized countries, including the widespread use of medications during pregnancy. Recent reports demonstrate that up to 70% of low risk patients used medications other than iron supplements (de Jong, 1991; Rodriguez-Pinilla, 1992).

With regard to perinatal and neonatal mortality, it has been shown that better outcomes are associated with higher numbers of antenatal care visits per mother (Ryan, 1980). These concurrent trends have been used as arguments to justify expanding programmes without regard to the fact that in general, lower risk women are more likely to seek care earlier. The general belief of obstetricians is exemplified in this opening sentence of an article: "It is now universally accepted that antenatal care is probably the most important factor which determines the outcome of pregnancy" (Nylader & Adekunle, 1990). Although this may be true for very high risk women, parallel or opposing trends in time do not, in themselves, imply a causal relationship for the overall population. This particular claim has never been evaluated scientifically.

In recent years, voices have been raised to redefine the quality of care, instead of increasing quantity (Bryce, 1990; Elbourne et al., 1989). The screening ability of several obstetric procedures for the diagnosis of small-for-gestational age showed to be remarkably low (Backe, 1993). In 1992, funds were granted in Scotland to compare alternative models of antenatal care delivery (Greater Glasgow Health Board, 1991). In the Netherlands, van Roosmalen & Gravenhorst (1992) have proposed a controlled trial to test the effect of fewer visits in a low risk population. The key issue is not more or less antenatal care or reducing the number of visits, but implementing only those activities proven to be effective; the frequency and timing of visits can then be planned accordingly.

The situation is obviously different between developed and developing countries. In the later, conditions vary greatly regarding both quality and quantity of care, and improvement of services ought to be a matter of high priority. With the deplorably high maternal (AbouZahr & Royston, 1991) and perinatal mortality and morbidity (Weekly Epidemiological Record, 1989) prevailing in many of the poorest countries and regions of the world, any improvement would be expected to have a significant impact.

According to the World Health Organization (1989), there is wide variation in the proportion of women who receive antenatal care, both between and within geographic areas. In Africa the figures ranged from 2% to 99% and in Asia from 8% to 98%. Surveys covering the years 1986 to 1989 from a number of developing countries revealed figures for antenatal coverage mainly ranging from 50% to 90% (Buekens, 1990; ICMP, 1991). Analyses demonstrated that in most of these countries, the more care provided, the better the perinatal conditions. While social and cultural constraints may be an obstacle to attendance in some instances, the major reason for non-attendance is lack of resources (skilled personnel and money) and quality of care (Sundari, 1992) on the part of care-providing authorities, and lack of money among care-receivers. In urban areas, there are usually several levels of antenatal care provision. Regardless of level, each programme is aimed at following the traditional pattern. Still, many women are seen only once or a few times before they go into labour. In many developing countries where services are available, the smaller average number of visits is largely due to late initiation of antenatal care rather than non-adherence to the recommended standards (Nylander & Adekunle, 1990).

Recent attempts were made to evaluate antenatal care proposals for low risk women (Chan, 1993; Gissler, 1994; Raine, 1994; Kogan, 1994; Munjanja et al., 1996; Sikorski et al., 1996). Only in two trials (Munjanja, 1996; Sikorski, 1996) were there a clinically significant reduction in the median number of visits. A trial from Zimbabwe (Munjanja et al., also suggests a reduction in the incidence of preterm delivery. A trial from the U.K. (Sikorski et al., 1996) demonstrates that a moderate reduction in the number of visits is not associated with an increase in any of the negative maternal or perinatal outcomes, but more women in the intervention group were less satisfied with the reduced number of visits

schedule. There have been six randomized trials evaluating the effect of enhanced prenatal care by relatively broad-based interventions as compared with standard care on birth weight. This expanded antenatal care includes strong psychosocial support and educational activities at the clinics or in home visits. Four of these studies, with a total sample of close to 7,000 women conducted in different countries, showed no demonstrable effect on birth weight or gestational age (Spencer et al., 1989; Heins et al., 1990; Bryce, 1991; Villar et al., 1992). It should be noted, however, that in the Heins et al study, nurse midwives were able to care for high risk populations as compared with highly trained obstetricians, without differences in the outcome variables. The other two, although reporting no overall effect on birth weight and the rate of low birth weight (McLaughlin et al., 1992; Olds et al., 1986), demonstrated a small positive effect in a subgroup analysis. In the Olds study, an improvement in birth weight was observed among 21 teenagers, as compared with eleven "comparable" control mothers. In the stratified analysis of 86 primiparous mothers assigned to the comprehensive programme, an increase of 144 gm was seen (McLaughlin et al., 1992). No effect was present among multiparae. The results of these small stratified analyses are not corroborated by a larger multi-centre study (Villar et al., 1992).

Overall, there were 10 studies that provided data on preterm delivery and 11 that included LBW and type of delivery as outcome variables. The meta-analysis of these studies yielded odds ratios of 0.93 (95% CI 0.82 to 1.05) for preterm delivery, 0.93 (95% CI 0.81 to 1.07) for LBW and 0.96 (95% CI 0.86 to 1.07) for forceps delivery or cesarean section.

